4.2 Exclusion Criteria

NH Participating in CHATO. Assisted Living facilities or other types of facilities are excluded as well as NHs that previously participated in the CHAT study.

Staff Participants. All staff are welcome to participate in the CHATO training, no staff exclusions.

4.3 Study Enrollment Procedures

For the R61, we partnered with seven Presbyterian Manor sites to pilot the CHATO intervention. These facilities have already been screened for eligibility and/or ineligibility. Letters of agreement will be collected from each NH as well as executive leaders from Presbyterian Manors. All staff at these sites will be invited to participate and will read and accept an exempt statement prior to taking the CHATO training.

5 STUDY INTERVENTIONS

5.1 Interventions, Administration, and Duration

CHATO is a direct Internet module adaptation of the CHAT program, developed by the PI and an instructional design team to include all CHAT content and interactivity. Standards for online education were used to transition to the module format. CHAT (and CHATO) have interchangeable content and are conceptually based on the Communication Predicament of Aging¹⁶ that describes how stereotypes of older adults as incompetent prompt younger persons (NH staff) to alter their communication with older adults (NH residents). The exaggerated simplification and clarification strategies of elderspeak result in speech that sounds like baby talk and is perceived as demeaning, contributing to isolation, depression, assumption of dependency, and BPSD.^{16,62} CHATO alerts NH staff to elderspeak and its negative effects, involves them in taking the older adult's perspective, and guides self-evaluation and practice of effective communication.⁶³ Improved communication, based on individual assessment of resident abilities, supports positive self-concept and meets socialization needs, reducing need-driven dementia-compromised behavior or BPSD.

CHAT and CHATO include review of actual NH video examples and practice of improved communication strategies that staff readily apply and monitor in practice, significantly reducing elderspeak in just three modules. Both CHAT and CHATO target adult learners using applied strategies tailored to improve specific aspects of elderspeak that are described in the literature and are modifiable. Limiting content and complexity minimizes burden to staff and their NH employers and increases the likelihood of skill enactment.⁶⁴

CHAT was developed step-wise and iteratively through the NIH Stage Model for Behavioral Intervention Development.⁶⁵ Early Stage 1 development led to Stage III testing of CHAT in controlled NH (community) settings to establish efficacy. After additional Stage I modification of the original CHAT content to online module format, CHATO is now positioned for effectiveness testing (Stage IV) with NH (community) providers to maximize external validity in preparation for future Implementation and Dissemination research (Stage V).⁶⁶

The CHATO program is presented in three modules.^{37,63} Session 1 introduces effective versus ineffective communication. Participants identify communication issues in video vignettes. Session 2 focuses on identification and negative effects of elderspeak, using video-recorded

examples. Session 3 includes strategies for improved communication based on assessment of each resident's abilities. Participants critique communication in videos and correct transcripts to eliminate elderspeak. Training is limited to three, 1-hour sessions to assure feasibility in busy NHs. The modules include interactive exercises that must be successfully completed to advance through the program, assuring delivery of content fidelity and dose of the intervention. CHATO is provided to as many staff as possible to achieve facility-wide effects of reduced elderspeak.⁶⁷

NH sites will receive the link to the trainings in three-month intervals according to the randomization plan. The NH leadership will determine the best method of implementation for their site. The link to the training will be shared with staff and the staff will have three months to complete all three modules. The modules contain pre and posttests (scenario-based questions and rating of staff communication in video clips) to evaluate knowledge gain from CHATO. The Modified Duke Diffusion of Innovation⁵⁸ survey provides information about CHATO participant intentions to use learned skills in practice and the likelihood for translation.

During the R61, the instructional designer will assure that data for identifying each participant's NH and metrics including time spent in each module are collected for analyses.^{34,37}

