Staff Knowledge Gain. At time 1, nursing home staff in both groups will complete baseline pre-tests of knowledge and rating of communication. The immediate intervention group will then complete the online CHATO modules within a one-month period. This includes assessments of post-test knowledge, communication rating, program evaluation, and diffusion of innovation surveys at Time 2. Also, at Time 2, the wait-list control group will repeat the pre-tests of knowledge and communication rating and will then complete the CHATO online module training over a one-month period, followed by Time 3 collection of post-test knowledge, communication rating, program evaluation, and diffusion of innovation surveys. Knowledge gain and communication rating data will be compared between the intervention and wait-list control groups and within nursing homes before and after the CHATO training. Changes in knowledge from Time 1 (baseline) to Time 2 will be compared between immediate and wait-list groups using model estimates obtained with a linear mixed model (LMM) approach to account for repeated measures and clustering within nursing homes. Next, pre- to post-training changes in knowledge will be combined for immediate and wait-list groups and also tested using LMM approach. The models will be adjusted for covariates, such as staff role (RN, LPN, CNA, other), experience, and whether the nursing home has a SCU or not.

TABLE 1. R61 Study Design

Group	Time 1	1 Month	Time 2	1 Month	Time 3
Immediate 3 NHs	Baseline assessment ¹	CHATO training ²	Post-training assessment ³		
Wait list 3 NHs	Baseline assessment ¹		Repeat baseline assessment ¹	CHATO training ²	Post-training assessment ³

¹Pre-test knowledge, Communication rating; ² Three modules over a one-month period;

³ Post-test knowledge, Communication rating, Program Evaluation, Diffusion of Innovation

Resident Quality Measure Outcomes. In addition, nursing homes in both groups will provide monthly summary reports for behavioral symptom occurrence for the facility (in aggregate as well as for individual residents [deidentified]). A nursing home aggregate antipsychotic medication use report will also be collected and analyzed. The BPSD and medication reports will

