6 STUDY PROCEDURES

6.1 Schedule of Pilot Evaluations in NHs

Assessment	Initial Leadership Meeting	Treatment CHATO Planning (1 st Month)	Treatment CHATO Training (2 nd Month)	Treatment CHATO Follow-up (3 rd Month)	Closing Leadership Meeting	Final Data Collection
NH Agreement	X					
Staff CHATO Participation		X				
Staff Demographics			X			
Staff CHATO Knowledge Pre-Test			X			
Communication Rating Sheet Pre-Test			X			
Staff CHATO Knowledge Post-Test			X			
Communication Rating Sheet Post-Test			X			
Modified Duke Diffusion of Innovation Intention Survey			X			
Staff CHATO Evaluation			X			
Implementation Survey				X		
The Artifacts of Culture Change Tool				X		
Staff Wage Data					X	
NH Level Resident Data						X
Leadership Phone Interviews						X

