6.2.3 Treatment: CHATO Training

The treatment schedule may vary according to the needs of each individual nursing home; however, all modules will be completed by as many staff as possible during the three-month intervention period. Technical assistance will be provided as needed.

- Treatment: CHATO Training Module 1
 - Staff Demographics
 - Communication Rating Sheet Pre-Test
 - CHATO Knowledge Pre-Test
- Treatment: CHATO Training Module 2
- Treatment: CHATO Training Module 3
 - Communication Rating Sheet Post-Test
 - CHATO Post-Test
 - Modified Duke Diffusion of Innovation Intention Survey

- CHATO Program Evaluation

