9.4 Data Analyses

SAS software⁷¹ will be used for all analyses. Initial analysis will calculate descriptive statistics at

all data collection points. Outliers will be investigated for accuracy and possible entry errors. Graphic representation of data and correlations among variables will be examined. Patterns and site effects of missing data will be examined in relation to variables of interest.⁷²

Knowledge gain and communication rating data will be compared between the intervention and wait-list control groups and within nursing homes before and after the CHATO training. Changes in knowledge from Time 1 (baseline) to Time 2 will be compared between immediate and wait-listed groups using model estimates obtained with a linear mixed model (LMM) approach to account for repeated measures and clustering within nursing homes. Next, pre- to post-training changes in knowledge will be combined for immediate and wait-list groups and also tested using LMM approach. The models will be adjusted for covariates, such as staff role (RN, LPN, CNA, other), experience, and whether the nursing home has a SCU or not. Distributions of residuals will be evaluated for normality and variance homogeneity and variables will be transformed as needed or statistical analyses for non-normal data will be utilized.

The BPSD and medication reports will be provided for the one-month period before baseline data collection and for each month thereafter until the post-training assessment of the wait-listed nursing homes is completed (a total of seven months for both groups). Resident outcomes data will be compared between the intervention and wait-list control groups and within nursing homes before and after the CHATO training. Seven months of data will be plotted to examine changes in nursing homes and resident outcomes.

We will analyze NH strategies used to engage staff in CHATO (approach, motivation, incentives). Strategies will be described, categorized, and correlated with participation rates. A survey for CHATO group NHs, will describe how CHATO was implemented and concurrent activities that may have influenced BPSD and psychotropic use rates. The Artifacts of Culture Change Tool will describe the NH care environment and practices, leadership and workplace practices, staffing outcomes, and occupancy.¹⁰⁰ In addition, a simple cost-effectiveness analysis (CEA) for the cost associated with hypothesized BPSD reductions will be calculated.

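### Section 6 gives wait-list homes one untrained knowledge test, but the randomised comparison in Section 9.4 needs two

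*Combined protocol and SAP*

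**What the plan says.** **Design and analysis.** Section 3 (Staff Knowledge Gain) states: "At time 1, nursing home staff in both groups will complete baseline pre-tests of knowledge and rating of communication". It continues: "Also, at Time 2, the wait-list control group will repeat the pre-tests of knowledge and communication rating". Table 1 and the matching table in the précis show the same for the wait-list arm: baseline at Time 1, repeat baseline at Time 2, post-training assessment at Time 3, one month apart. Section 9.4 builds the randomised analysis on this: "Changes in knowledge from Time 1 (baseline) to Time 2 will be compared between immediate and wait-listed groups", using a linear mixed model. A second analysis follows, in which "pre- to post-training changes in knowledge will be combined for immediate and wait-list groups".

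**Operations.** Section 5.1 states: "The modules contain pre and posttests (scenario-based questions and rating of staff communication in video clips) to evaluate knowledge gain from CHATO". Section 6.1 is a single schedule for both arms. All staff tests stand in the column for the home's own training month, once each. The planning month before it holds one entry, "Staff CHATO Participation". Section 6.2.3 agrees: "CHATO Knowledge Pre-Test" and the communication rating pre-test appear once, under Module 1, and the post-tests once, under Module 3. Section 6.2.2 obtains the letter of agreement and the staff email list at the meeting that opens the home's own three-month period. Table 5 lists two forms of the knowledge test, A and B.

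**Related windows.** Sections 3 and 9.4 call for monthly resident reports over seven months in both groups; Section 6.2.4 gives one month before training and one month after. Table 1 puts training, and the gap from Time 1 to Time 2, at one month. Section 3 (Implementation Strategies) puts one training month inside a three-month period. Section 5.1 releases links at three-month intervals and allows three months for the modules.

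**The concern.** A wait-list arm shows what happens to untrained staff over the interval in which the other arm trains. That takes two untrained scores. The sections that sites and the Moodle build will follow provide one, and they place first enrolment contact with a wait-list home at the start of its own period. No visible operating section says how its staff are reached or tested at Time 1.

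At stake is the only randomised analysis of change in the primary outcome. An untrained Time 1 score cannot be collected after training. Section 10.3.5 checks data collection against the protocol, so a team working from Section 6 would have no prompt to notice that it was missing.

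**Working it through.** The plan gives no alpha, power or effect size for this comparison, so there is no stated figure to reproduce. The check is a count, then a question of identification.

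**1. Wait-list test occasions**

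| | Time 1 | Time 2 | Time 3 | All | Untrained |
|---|---|---|---|---|---|
| Section 3, Table 1 | test | test | test | 3 | 2 |
| Sections 6.1, 6.2.3 | none | Module 1 pre-test | Module 3 post-test | 2 | 1 |

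The Module 1 pre-test can serve as Time 2. Nothing in Section 6 serves as Time 1.

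**2. Does the stagger between arms matter?** Let the wait-list period start s months after the immediate arm's, with the planning, training and follow-up months of Section 6.1. The immediate baseline is then at month 1 and the wait-list opening meeting at month s.
- s = 1 (an assumption that fits Table 1): the meeting coincides with Time 1 (1 − 1 = 0). The home is in its planning month, where Section 6.1 shows only the staff list.
- s = 3 (Section 5.1): the letter and emails arrive 3 − 1 = 2 months after Time 1.

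Untrained wait-list scores number one in both cases.

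**3. Identification.** Write I1, I2, W1, W2 for the mean scores by arm and time.
- Section 9.4 contrast: (I2 − I1) − (W2 − W1). With W1 never observed, three of four cells are filled and the group-by-time term is not identified. A mixed model can handle scattered missing scores; it cannot supply an empty cell.
- Assuming W1 = I1, the contrast reduces to I2 − W2, a comparison of levels.

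**4. What each contrast estimates.** Let T be the training gain, g the gain from taking the test a second time, and d the baseline difference between arms (immediate minus wait-list).
- As designed: (T + g) − g = T, if g is the same in both arms.
- Levels under Section 6: I2 carries T + g and W2 is a first test, so I2 − W2 = d + T + g.
- Pooled pre/post: T + g, with no concurrent control.

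The documents give no value for g. The nine-person test in Section 2.2 rose by 91.21 − 82.4 = 8.81 points, but it had no untrained retest group, so that rise is itself T + g and cannot be split.

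**5. Precision (illustration only).** Assume an SD of 10.62 (that same nine-person sample), k = 3 homes per arm, m = 150/6 = 25 staff per home, ICC 0.01 to 0.10, within-person correlation r from 0.3 to 0.7, home-level correlation over time c from 0.5 to 0.8, two-sided 5%, 80% power and t on 4 df. With Vb = ICC × SD² and Vw = (1 − ICC) × SD²:
- Levels: SE = √[(2/k)(Vb + Vw/m)] = 1.93 to 3.20; detectable difference 7.2 to 11.9 points.
- Change: SE = √[(2/k)(2Vb(1 − c) + 2Vw(1 − r)/m)] = 1.44 to 3.36; detectable difference 5.4 to 12.5 points.

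The ranges overlap. The point therefore rests on what can be estimated, not on power.

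**6. Resident reports.** Six homes × 7 months = 42 home-months (Sections 3, 9.4). If Section 6.2.4 means two single months per home, 6 × 2 = 12.

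**The case against.** The strongest reply is that the Time 1 test is planned. The précis, the Section 3 text and Table 1 all contain it, and Section 9.4 analyses it. Sections 6.1 and 6.2.3 can be read as describing a home's own training period, without regard to arm. The Section 5.1 sentence says where tests sit and does not exclude another sitting. Table 4 lists forms and collection routes, not occasions. Manuals and appendices are not visible. All of this stands. A reader might infer that the plan never schedules a wait-list baseline, and that would be wrong: the design sections schedule it and the operating sections omit it.

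A reader might also infer that no randomised comparison would survive. That goes too far. Immediate post-test against wait-list pre-test still compares randomised arms, and randomisation makes baselines equal in expectation. But with three homes per arm the realised difference d could be material and could not be checked, and g stays in the estimate.

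Three further inferences are not supported.
- *The surviving comparison would be about two months out of step.* This follows from Section 6.1's months with a three-month stagger (4 − 2 = 2). On the clock that fits seven months of reports (1 + 3 + 3 = 7), immediate post-test and wait-list pre-test both fall at month 3 and the gap is zero. The documents do not settle which clock applies.
- *The arms would share no month of resident data under Section 6.2.4.* That needs two isolated months per home and particular staggers. Read as the outer limits of a window, the same wording gives overlap.
- *Homes could choose staff knowing their allocation.* Homes are randomised before staff are listed, but Sections 4.3 and 6.2.1 invite all staff, which limits this. It is a separate matter.

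Finally, this is a pilot with no power claim. That lowers the stakes, but preliminary efficacy is the stated aim and this comparison is its randomised evidence.

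**Conclusion.** The plan is wrong as written on this point. Section 3, Table 1 and Section 9.4 contradict Sections 6.1, 6.2.2 and 6.2.3: three wait-list test occasions are required and two are scheduled; two untrained occasions are required and one is scheduled. The count does not depend on the stagger between arms. If the team follows Section 6, the Section 9.4 change contrast can be estimated only by assuming equal baselines across two arms of three homes, and even then the result is training gain plus retest gain. If the team follows Section 3, the comparison is sound in this respect. The conclusion assumes that no unseen manual or appendix already supplies the wait-list Time 1 sitting. The size of the retest gain is unknown.

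The conflict over resident-data months, and that between Table 1's one-month gap and Section 5.1's three-month intervals and completion time, are real but secondary.

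**What to change.** Before Time 1, amend Sections 6.1, 6.2.2 and 6.2.3:
- Obtain letters of agreement and staff lists from the three wait-list homes before Time 1.
- Give wait-list staff the knowledge test and communication rating at Time 1, outside the modules, at the same time as the immediate arm's baseline.
- Keep the Module 1 pre-test as wait-list Time 2, timed to match the immediate arm's post-test.
- Show Time 1, 2 and 3 by arm in Section 6.1.
- State which of Forms A and B is used at each of the three wait-list occasions; with two forms, at least one must be used twice.

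Also reconcile two windows:
- Resident data: Sections 3 and 9.4 against Section 6.2.4. The plots and between-arm comparison in Section 9.4 need the monthly series.
- Training and test spacing: Table 1 against Section 5.1. Which applies is the sponsor's choice.

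The cost is protocol wording, a small Moodle set-up change, one extra short online sitting for wait-list staff, and earlier contact with three homes that are already partnered and screened.

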5.2 Handling of Study Interventions

The study intervention is the Changing Talk Online (CHATO) training. The goal of course is to increase awareness of the importance of effective communication with older adults and to use evidence-based person-centered communication during interactions with older adults in nursing homes and other health care settings. The course is designed for staff in nursing homes, independent and assistive living, and health care settings in the community that include registered nurses, nursing assistants, nursing home dieticians, direct care professionals, other administrations and support employees. The total program is approximately 3 hours, split into 3 modules. Each module is approximately an hour, depending on the individual user. Upon completion of all three modules and 70% on a posttest, a certificate of completion (3 nursing contact hours) will be awarded.

Treatment 1: CHATO Training Module 1

This module contains information on the importance, benefits, and components of effective communication. This module covers the overarching goals and objectives, the benefits and components of effective communication, communication challenges of aging, and identification of effective communication (Videos).

Learning Outcomes

- Recognize the importance of communication to older adults.
- Identify barriers to communication in care of older adults.
- Distinguish between effective and ineffective communication strategies

Treatment 2: CHATO Training Module 2

This module contains information on common communication barriers and challenges, elderspeak communication, and effective and ineffective communication strategies. It reviews benefits and components of effective communication and introduces Elizabeth Layton paintings and thought exercises. The module also covers communication barriers and nursing home communication, ignoring talk vs. task talk vs. interpersonal talk, the Communication Predicament Model and elderspeak, and the identification of elderspeak and ineffective strategies (Videos).

Learning Outcomes

- Identify elderspeak and its potential negative messages.

- Contrast effective and ineffective communication strategies.
- Revise transcripts to reduce elderspeak and ineffective communication.

Treatment 3: CHATO Training Module 3

This module contains information on common problems during communication, guidelines for improving communication, and characteristics of person-centered communication. The modules review nursing home communication, ineffective strategies, and elderspeak and discusses the Communication Enhancement Model. Affirming and effective communication and evaluating communication are practiced (Videos and Rewriting of Scripts).

Learning Outcomes

- Identify affirming communication.
- Critique communication in video recordings of nursing home staff-resident communication.
- Rewrite transcripts to reduce elderspeak and ineffective communication.

The course content is presented by [name], RN, PhD. There are learning activities, discussion forums, list of resources, pre and posttests, and evaluations at the end of the course. The practice activities were designed to provide opportunities to apply the knowledge and skills presented in the course and a virtual discussion forum is available to share experiences and reflect with others.

